However, as a preliminary assessment of power, we consider the power of a paired t-test comparing pre- and post- intervention scores on the various response measures, including survey scales, cortisol, and HRV. We compute power in terms of Cohen's d, a standardized effect size measure that describes the impact of the intervention in terms of the number of standard deviations that the effect is equivalent to (so an effect of 5 points on a scale with SD 20 would have a Cohen's d of 0.25). On this scale, an effect size of 0.2 is typically considered "small", 0.5 "moderate", and 0.75 "large". This may not align with clinically meaningful differences in outcome measures, however.

For comparisons within intervention groups in their first (and sometimes only) year of intervention, we expect to have 30 participants in each group (Livingston students, Livingston teachers, rural students, rural teachers). Assuming a Type I error rate of $\alpha = 0.05$, we achieve 80% power to detect a Cohen's d of 0.53, and 90% power to detect a Cohen's d of 0.61. Thus, the study is adequately powered to detect moderate-to-large effects of the intervention. The study design will allow us to estimate the magnitude of effects, intra-class correlations by school and classroom, and the variability of intervention impacts—all the inputs needed to perform a formal power analysis for a future Phase III trial. Full power curves for $n = 30$ and $n = 15$ participants are given in Figure 1.

[figure not shown]

Figure 1. Power curves for sample sizes of 15 and 30. Solid black line indicates 80% power and dashed line indicates 90% power.

Statistical Analysis Plan

For each outcome, we will compute the change in the scale score or biomarker value from baseline to post-intervention (post – pre) and compute unadjusted averages and standard deviations. These computations will be done within participant group (Livingston students, Livingston teachers, rural students, rural teachers).

We will also obtain adjusted estimates using mixed effects linear regression models of post-test score on pre-test score with demographic factors and random effects for school and intervention group nested within school (Laird & Ware 1982). This will allow us to estimate intra-class correlations for intervention group and school, which will be required for sample size estimation in a full efficacy trial.

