We propose the following model for the individual response (anxiety, depressive symptoms, etc.), denoted Y_{ijk} , where $i = 1, \dots, I$ indexes school, $j = 1, \dots, J$ indexes intervention group (only needed if there are multiple health education classes receiving the intervention in a school), and $k = 1, \dots, N$ indexes participants within groups.

$$\begin{aligned}
 Y_{ijk} &= Z_{ijk} \theta + X_{ijk} \delta + \alpha_i + \beta_{j(i)} + \varepsilon_{ijk} \\
 \alpha_i &\sim N(0, \tau^2) \\
 \beta_{j(i)} &\sim N(0, \omega^2) \\
 \varepsilon_{ijk} &\sim N(0, \sigma^2)
 \end{aligned}$$

Thus, α_i represents a random effect for school i , with variance τ^2 , $\beta_{j(i)}$ represents a random effect corresponding to group j in school i , with variance ω^2 . We model this as a function of Z_{ijk} , the pre-intervention score for participant k in group j in school i , and X_{ijk} , the set of other modeled covariates, centered at their means. This means that the intercept parameter θ gives the expected effect of the program for a student or teacher with “average” demographics and other covariate values after controlling for within-school and within-group correlation. We can use the estimates of the random-effects variances and the residual variance to produce estimates of the intra-class correlations for school and for intervention group.

This is a Linear Mixed Effects (LME) model. As all primary and secondary response variables are continuous and may reasonably be expected to be normally distributed we can implement the model using restricted maximum likelihood (Laird & Ware 1982) using the `lme4` package in **R** (Bates et. al., 2015).

Biomarker analyses. Salivary cortisol and HRV will also be collected mid-intervention.

To fully characterize temporal patterns in these outcomes, we will use a different LME model that captures the full trajectory over time. In this case, we propose the following model for the individual response, denoted Y_{ijkt} , where $i = 1, \dots, I$ indexes school, $j = 1, \dots, J$ indexes intervention group (only needed if there are multiple health education classes receiving the intervention in a school), $k = 1, \dots, N$ indexes participants within groups, and $t = 1, \dots, 3$ indexes the time point of the observation.

$$Y_{ijkt} = \theta T_{ijkt} + X_{ijk} \delta + \alpha_i + \beta_{j(i)} + \gamma_{k(ij)} + \varepsilon_{ijkt}$$

$$\alpha_i \sim N(0, \tau^2)$$

$$\beta_{j(i)} \sim N(0, \omega^2)$$

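### The pre/post mixed model prints θ as the slope on the pre-score but describes it as the intercept and program effect; neither θ nor an added intercept is a pre-to-post change

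*Combined protocol and SAP*

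**What the plan says.** All references are to the combined protocol and SAP.

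- **Unadjusted summaries (Statistical Analysis Plan, opening paragraph).** "For each outcome, we will compute the change in the scale score or biomarker value from baseline to post-intervention", taken as post minus pre and summarised within each participant group.
- **Adjusted estimates (next paragraph).** These come from "mixed effects linear regression models of post-test score on pre-test score", with demographic factors and random effects for school and for intervention group within school. The stated purpose is: "This will allow us to estimate intra-class correlations for intervention group and school".
- **Equation for the individual response.** The fixed part, followed by the school effect, is printed as "Z_{ijk} \theta + X_{ijk} \delta + \alpha_i". Both random effects have mean zero and there is no separate constant.
- **Definitions under the equation.** "We model this as a function of Z_{ijk} , the pre-intervention score for participant k", and X is "the set of other modeled covariates, centered at their means".
- **Interpretation.** "This means that the intercept parameter θ gives the expected effect of the program", for a person with average covariate values.

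The power section does not use this model: "we consider the power of a paired t-test".

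**The concern.** The equation and its interpretation assign θ two different roles. In the equation θ multiplies the pre-intervention score. In the text it is a constant equal to the program effect. No other term can supply that constant, because X is centred and the random effects have mean zero.

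Printing an intercept would not be enough. The response is the post-test score, so an intercept is a post-score level: at a pre-score of zero if Z is uncentred, or at the mean pre-score if Z is centred. The centring clause can be read as covering X only or both Z and X.

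The sentence on θ is the SAP's only definition of the adjusted program effect for the pre/post outcomes. The Power considerations section counts effect magnitudes and intra-class correlations among the inputs for a future Phase III power analysis. An analyst who followed the sentence would report a slope or a score level in place of a change.

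**Working it through.** **The plan's own figures.** A two-sided paired t-test with n = 30, 29 degrees of freedom and noncentrality d√30 has power 80.1% at d = 0.53 and 89.8% at d = 0.61. The stated 80% and 90% reproduce. They do not involve θ.

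**What θ is as printed.** At average covariates and zero random effects, the equation gives E[post | Z = z] = θz. So θ is a unitless slope.

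**Assumed inputs.** The documents give no score distributions. Assume pre-score mean m = 8, SD s = 5 before and after, and pre-post correlation r = 0.7. The post mean is then 8 with no true change, or 5.5 with a change of -2.5.

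**Closed forms, no school effect fitted**

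| Reading | Formula | No change | Change -2.5 |
|---|---|---|---|
| θ as printed, Z uncentred | (r·s² + m·m_post)/(m² + s²) | (17.5 + 64)/89 = 0.92 | (17.5 + 44)/89 = 0.69 |
| θ as printed, Z centred | r | 0.70 | 0.70 |
| Added intercept, Z uncentred | m_post - r·m | 8 - 5.6 = 2.4 | 5.5 - 5.6 = -0.1 |
| Added intercept, Z centred | m_post | 8.0 | 5.5 |
| Mean change (target) | m_post - m | 0 | -2.5 |

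With Z centred, the printed θ is 0.70 whatever the program does. The intercept with uncentred Z equals the mean change only if the slope is exactly 1. For m from 4 to 12 and r from 0.5 to 0.8 with no true change, the four readings span 0.70 to 0.97, 0.50 to 0.80, 0.8 to 6.0, and 4 to 12.

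**With the printed school effect.** The school term takes up part of the missing constant, so 0.92 is not quite what the printed model returns. Simulated trials of n = 30 with no true change were fitted by REML (not lme4), with three schools of 5, 10 and 15 or five of 6, and school variance 0 or 2; these are also assumptions. θ averaged 0.81 to 0.87 with Z uncentred and about 0.70 with Z centred.

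**Intra-class correlation.** The residual variance is 25 × (1 - 0.49) = 12.75. The true school ICC is therefore 0, or 2/(2 + 12.75) = 0.14.

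| Fit, no true change | Average estimated school ICC |
|---|---|
| No intercept, Z uncentred | 0.12 to 0.25 |
| No intercept, Z centred | about 0.83 |
| Intercept included | 0.04 to 0.15 |

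The centred figure follows from the school effects absorbing a missing mean of 8: 64/(64 + 12.75) = 0.83. With uncentred Z the inflation depends on the missing constant. That constant is 2.4 here but only -0.1 for a change of -2.5, where little inflation is expected.

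**Check of the repair.** In the same setting, an intercept μ for post minus pre with centred Z averaged -0.01 to 0.03 with no true change. It equals the post-score intercept (Z centred) minus the sample pre-score mean, and the two forms give the same ICCs.

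**The case against.** The strongest reply is that this is a slip of notation. Calling θ an intercept shows that a constant was intended, and lme4 adds one unless told not to. The model is introduced mainly to estimate intra-class correlations, no test, interval or decision rule is attached to θ, and the unadjusted changes are clearly defined. A reported value of 8.0 would look odd beside a raw change near zero. The SAP also promises adjusted estimates and an expected program effect; it does not use the term adjusted mean change.

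Most of this stands, and it limits the harm. It does not remove the point, because supplying the intended intercept still gives a post-score level. Change is the natural scale for the adjusted effect because the SAP pairs these estimates with unadjusted changes.

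A reader might go further in two ways that the documents do not support. One is that the planned ICCs are invalid. That follows only from a literal fit without an intercept. The other is that the plan's confidence intervals are too narrow. The SAP specifies no interval for this parameter, so there is none to fault.

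**Conclusion.** The point holds and should be fixed. The equation and the text contradict each other on what θ is, and neither the printed θ nor an added intercept is a program effect on the post-minus-pre scale. That conclusion is algebraic and needs no assumed numbers. The sizes do: they rest on the assumed pre-score mean, SD, correlation, school layout and school variance.

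The consequence is limited to the adjusted pre/post effect and, only if no intercept is fitted, to the ICCs. The documents do not support the inference that the adjusted analysis as a whole, or the study's power, is unsound.

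**What to change.** Replace the equation with

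(post - pre)_ijk = μ + (Z_ijk - mean Z)λ + X_ijk δ + α_i + β_j(i) + ε_ijk, with X centred.

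Replace the sentence about θ with: *μ is the adjusted mean pre-to-post change at the average pre-score and covariates; with no comparator it is not a causal effect.*

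Equivalently, keep the post-test response with an intercept and centred Z, and report the intercept minus the sample pre-score mean.

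If an interval for the population mean change is reported, note that the model-based standard error is conditional on the observed pre-scores. Any added term λ²·s_Z²/n must use the slope from the change-score model, which is the post-score slope minus 1. Without covariates or a school effect, using the post-score slope instead would make the standard error too large by a factor of √(1/(2(1 - r))): 1.29 at r = 0.7 and 1.58 at r = 0.8.

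The cost is SAP wording and one line of code. No new data are needed, and the ICCs do not change relative to a model that already has an intercept.

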A Trauma-Informed Intervention for Positive Youth Development and
Teacher Wellness in Rural Montana

[name]

September 1, 2021

Clinical Trial # NCT05085392

Statistical Design and Power

Study design

This study is a non-randomized, Phase I clinical trial. Participants will be high school students and teachers in southwest Montana. In the first year, 30 teachers from the same school district will be recruited to participate in a virtually-delivered trauma-informed yoga intervention (heart rate variability data will be gathered from a group of high school students to assess utility for the measure in year 2). In the second year, we will expand the intervention to high school students in Livingston city and rural Park County schools, recruiting 30 students in each area to participate in a synchronous, virtually-delivered, trauma-informed yoga intervention during their health enhancement classes. In addition, 30 teachers from the rural Park County schools will be recruited to participate in the same virtually-delivered, trauma-informed yoga intervention offered to Livingston teachers concurrently.

In each year, participant assessments (surveys, salivary cortisol, and heart rate variability(HRV)) will be administered prior to intervention and immediately after the intervention at 6 weeks. Follow-up assessments will be conducted in the fall semester following each intervention to measure persistence of the treatment. Thus, Livingston teachers may have up to six time points of data collection, while Park County students and teachers and Livingston students will have up to three. In addition, salivary cortisol and HRV will be collected at the midpoint of the intervention (3 weeks) each year. Measures collected are detailed in Table 1.

Table 1. Measures recorded for students and teachers, with collection timeline and validity measures.

Description of Measure	Source (if applicable)	Timeline for Collection	Cronbach's Alpha/Validity & Reliability
Center for Youth Wellness ACE-Q Self-Reporting Screener for Teens (Adolescents Only)	Burke-Harris & Renschler, 2015	Pre-intervention (in order to determine ACE scores of participants)	Longitudinal testing currently underway to measure content and construct validity/reliability
Generalized Anxiety Disorder Scale (GAD-7) (Adolescents and Teachers)	Spitzer et al., 2006	Pre- and post-intervention	Cronbach's alpha: .79-.91 Reliability = .85 Validity = 73.3%

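### With every group treated, the plan estimates pre-to-post change, not a program effect, and that change should not become the Phase III target effect

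*Combined protocol and SAP*

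**What the plan says.** Study design states: "This study is a non-randomized, Phase I clinical trial". Both student groups are treated ("recruiting 30 students in each area to participate in a synchronous, virtually-delivered, trauma-informed yoga intervention"), and so are both teacher groups: Livingston teachers are recruited in year 1, and in year 2 "30 teachers from the rural Park County schools will be recruited to participate in the same virtually-delivered, trauma-informed yoga intervention". Surveys and biomarkers "will be administered prior to intervention and immediately after the intervention at 6 weeks", with a further assessment in the following fall.

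The Statistical Analysis Plan gives three analyses:
- average post-minus-pre change within each of the four groups;
- a mixed model of post-test on pre-test score, with demographics and random effects for school and for group within school;
- for cortisol and HRV, a mixed model over three time points.

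Of the second model it says that θ "gives the expected effect of the program for a student or teacher with" average demographics and covariates, once within-school and within-group correlation is accounted for. Power considerations says: "The study design will allow us to estimate the magnitude of effects", and adds that this, with the intra-class correlations and the variability of impacts, is everything a Phase III power analysis needs. Neither section warns that the change may have sources other than the program.

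**The concern.** A program effect is the difference between what happened and what would have happened without the program. Nothing in this design observes the second quantity. The outcomes are self-reported symptoms, resilience, teacher self-efficacy, cortisol and HRV, measured in school populations six weeks apart. Such measures could shift with the school calendar or with being completed a second time. Whatever shift occurs is added to the program's contribution, and the two cannot be separated.

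Two things are at stake. The trial's conclusion would attribute to the program a change that may partly or wholly be something else. And a later trial with a comparator, in which a shift common to both arms cancels, would be sized on an effect that is too large or too small by the amount of that shift.

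**Working it through.** **1. Is there any untreated reference?** Two features come near one.
- In year 1, "heart rate variability data will be gathered from a group of high school students to assess utility for the measure in year 2". This tests the measure, is not named as a comparator, and covers HRV only.
- Table 1 takes attendance and office-referral data for 8 weeks before the study and 8 weeks during it. That is itself a before-after comparison, and it does not cover the survey scales, cortisol or HRV.

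Neither supplies a control. The fall assessment does not either: "Follow-up assessments will be conducted in the fall semester following each intervention to measure persistence of the treatment" describes one more uncontrolled time point.

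**2. Do the models remove non-program change?** Write the mean change as Δ = p + b, where p is the program's contribution and b is everything else shared by participants. The post-minus-pre average estimates p + b. The school and group random effects have mean zero and describe how units differ from one another, so a shift common to all units stays in the fixed part. The biomarker model has a time term, but with everyone treated that slope is also program plus background.

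**3. What is θ?** In the printed equation θ multiplies Z, the pre-test score, so it is a slope. The text calls it the intercept. As the intercept of a post-on-pre model it would be an expected post-test score. It is a mean change under neither reading, so relabelling θ would not be enough. This is a separate fault from the missing comparator, but the fix has to allow for it.

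**4. Reproduce the plan's power.** Inputs from Power considerations: paired t-test, n = 30, α = 0.05. Sidedness is not stated; two-sided reproduces the figures. Power = P(|T| > 2.045), with T noncentral t on 29 df and noncentrality d√30.
- d = 0.53: noncentrality 2.903, power 80.1% (plan: 80%).
- d = 0.61: noncentrality 3.341, power 89.8% (plan: 90%).

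The arithmetic is right. It is power to detect any mean change, whatever its cause.

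**5. Same test with p = 0 and drift b.** b is in SD-of-change units and is assumed; the documents give no value.

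| b | b√30 | Chance of p < 0.05 |
|---|---|---|
| 0 | 0 | 5.0% |
| 0.1 | 0.548 | 8.3% |
| 0.2 | 1.095 | 18.5% |
| 0.3 | 1.643 | 35.6% |
| 0.4 | 2.191 | 56.3% |
| 0.5 | 2.739 | 75.4% |

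**6. Knock-on for a two-arm trial.** Assume an observed change of 0.5 SD, of which 0.2 is drift, so the true effect is 0.3. Two-sample t-test, two-sided 5%, 80% power, 1:1, individually randomized, change-score outcome.
- n per arm ≈ 2(1.96 + 0.8416)²/d². For d = 0.5 this is 62.8; the exact t calculation gives 63.8, so 64. For d = 0.3 it is 174.4; exact 175.4, so 176.
- Power at d = 0.3 with 64 per arm: noncentrality 0.3√(64/2) = 1.697, power 39%.

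Starting from the plan's own d = 0.53 (56 per arm by the normal approximation), drift of 0.1, 0.2 or 0.3 leaves 62%, 41.5% or 23% power.

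**7. Dependence on the outcome scale.** The per-arm numbers in step 6 hold for change scores, or for post scores if the pre-post correlation is 0.5. At an assumed correlation of 0.7, the SD of change is √(2 × 0.3) = 0.775 of the post-score SD, and 64 and 176 become about 106 and 292. The power loss hardly moves if the effect is converted consistently, because it depends on the ratio of true to assumed effect: 0.3/0.5 = 0.6, and Φ(0.6 × 2.80 − 1.96) = Φ(−0.28) ≈ 39%.

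**The case against.** The best defence is that this is openly a non-randomized, early-phase study, for which a single arm is legitimate. That stands, and the point does not ask for a control arm. The plan also disclaims power for small effects and notes that standardized effects may not match clinically meaningful differences. Neither caution concerns non-program change.

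Three further objections limit how far the point goes.
- The Statistical Analysis Plan specifies no significance test or success criterion; the paired t-test appears only in the power section. A reader might infer from step 5 that the trial has a false-positive rate of 19% to 75%. The documents do not support that: the figures describe a test the plan does not commit to, under assumed drift.
- A reader might also infer that regression to the mean is built into the results. No entry threshold on any score is described, and the ACE-Q is collected only to establish ACE scores. Regression to the mean is possible if volunteers enrol at unusual levels, but it is not shown. Calendar drift and repeat testing need no such selection, but their size is unknown too.
- It would go too far to say that nothing here can inform Phase III. Outcome SDs, the pre-post correlation and the intra-class correlations do not need an untreated group in the way an effect size does, and estimating the intra-class correlations is a stated purpose of the model.

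Planners might discount the estimate on their own initiative, but the document does not say that they will.

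**Conclusion.** The concern holds as a fault of interpretation and of one planning input. The plan describes an uncontrolled change as a program effect and offers its magnitude for Phase III, and the design cannot support either use. That conclusion rests on the documents alone and needs no assumed number.

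The size of the consequence does rest on assumptions: 19%, 36% or 75% significant results under drift of 0.2, 0.3 or 0.5 SD of change with no program effect, if the paired t-test were used; and about 39% power instead of 80% if 0.2 of an observed 0.5 SD were drift, before cluster inflation and assuming that Phase III has a comparator, which the documents do not state. Drift could equally mask a real benefit. Nothing here shows that drift will occur, that the program is ineffective, or that the single-arm design is improper. The correction should be made before results are reported.

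**What to change.** 1. **Statistical Analysis Plan, individual-response model.** Delete the statement that θ is the program's expected effect. Report instead the model-based mean pre-to-post change at average covariates, for example the intercept of a model of post minus pre on mean-centred pre-score and mean-centred covariates with the same random effects. State that this change is not attributable to the program alone.
2. **Power considerations.** Replace the reference to the magnitude of effects with magnitude of pre-to-post change. Use the same term wherever the section speaks of effects of the intervention, its impact, or the variability of its impacts. Remove the claim that all Phase III inputs are supplied.
3. **Use in Phase III.** State that Phase III planning will take the outcome SD, the pre-post correlation and the school and group intra-class correlations from this study, but not the uncontrolled mean change as its target effect. The target will be a pre-specified meaningful between-group difference for each outcome.

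The cost is wording and a small change of model parameterization, with no added participants or procedures. The downside is that the stated conclusion becomes less favourable.
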